13. MEDICAL MONITORING

An independent Medical Monitor, with a diverse therapeutic background, both clinical and research expertise, and an active medical license (preferably as a urologist), will be implemented in the study to provide medical and safety oversight as follows:

- Providing input into the study protocol, informed consent forms, riskassessment
- Supporting investigational sites with queries around patient eligibility, safety, etc.
- Reviewing subject safety data to identify trends and risks across the study
- Reviewing safety narratives as requested

14. PROTOCOL DEVIATIONS

A Protocol Deviation (PD) is defined as any alteration or modification to the approved protocol(s). This includes detailed Clinical Study Protocol, protocol summary, and the approved subject Informed Consent Form. A PD is any incident for which the Investigator or site personnel did not conduct the study according to the clinical protocol or the investigator agreement.

Deviations shall be reported to the study sponsor regardless of whether the deviation was medically justifiable, a study oversight, or taken to protect the subject in an emergency. Subject specific deviations will be documented on the Protocol Deviation CRF in the EDC system. Non-subject specific deviations will be reported to the Sponsor in writing (often via a note to file). Investigators will also adhere to procedures for reporting study deviations to their IRB in accordance with their specific IRB reporting policies and procedures.

Good Clinical Practices (GCP) regulations require that Investigators maintain accurate, complete and current records, including documents showing the dates and reasons for each deviation from the protocol. Protocol deviations will be captured in the EDC.

CONFIDENTIAL Page 44 of 53

15. STUDY MONITORING PLAN

The monitoring for this study will be conducted by Sponsor or designee. The study will be monitored, in accordance with the Acoustic Enhancer Research on Laser Lithotripsy (AEROLITH) Clinical Study Monitoring Plan (CLIN-0006), to ensure that the protocol, applicable regulations, and Good Clinical Practice Guidelines are followed. Study monitoring will be carried out in compliance with FDA regulations (21CFR Part 812), ISO 14155, and all GCP guidelines. The study monitor will ensure that the rights and well-being of subjects are protected and the clinical trial data are accurate, complete, and verifiable.

Prior to subject enrollment, the Sponsor or designee will obtain the essential regulatory documents required to initiate the study. The sponsor will be responsible for the review and approval of these essential documents. Copies of the documents will be maintained by the Sponsor.

Site Qualification/Initiation Visits

All sites will undergo a qualification process to confirm acceptability for participation into the study.

Study initiation visits are performed at the start of the clinical study to ensure that the study personnel have a complete understanding of the protocol, procedures, responsibilities, and regulations involved with the conduct of a clinical trial. Study personnel will be trained on all essential aspects of the trial prior to the first subject being enrolled in the study. This training will include an in-depth review of the protocol and case report forms, regulatory requirements, serious adverse experience reporting, and other activities as documented in the site initiation plan.

Interim Monitoring Visits

Interim monitoring visits will be made at all active investigational sites throughout enrollment of the clinical study to assure that the Investigator obligations are fulfilled and all applicable regulations and guidelines are being followed. These visits will assure that the facilities are still acceptable; the study protocol and related required protocols are being followed, the IRB has been notified of approved protocol changes as required, complete records are being maintained, appropriate and timely reports have been made to the Sponsor and the IRB, device and device inventory are controlled and the Investigator is carrying out all agreed activities. The monitor will verify accuracy of CRF completion against source documents maintained at the site.

During monitoring visits, the Monitor will perform a review of study eligibility, Inclusion/Exclusion criteria, informed consent, all reports of device malfunction, all events meeting criteria for serious adverse event reporting as well as safety and efficacy endpoints.

The monitor will periodically, at a minimum of annually, monitor the study sites. The investigator and staff are expected to cooperate and provide all relevant study documentation to the monitor upon request, including direct access to the study data, such as electronic medical records. In the event direct access is not provided to the monitor, certified printed copies may be accepted. Corresponding source data and documents are required to verify the accuracy of all data.

Site Close Out Visit

Upon completion of the clinical study (when all subjects enrolled have completed the follow-up visits and the CRFs and queries have been completed), a study closeout visit will be performed. The Monitor will ensure that the Investigator's regulatory files are up to date and complete and that any outstanding issues from previous visits have been resolved. Other topics which may be reviewed at this visit include: discussing retention of study files, possibility of site audits, publication policy, and IRB study closure notification.

CONFIDENTIAL Page 45 of 53

Qualifications of Study Monitor

Applaud Medical will select a study monitor qualified by training and experience to monitor the progress of the investigation. The proposed study monitor has suitable academic training, applicable clinical experience, and knowledge of the investigational device.

16. DATA MANAGEMENT

16.1. Data Collection

Study data will be collected by electronic Case Report Forms (eCRFs). Data queries and data updates will also be electronic. Source document verification (SDV) will also be electronic in the database. The investigator signature will also be electronic in the database. Each Patient will be assigned a unique deidentified study identification (ID). All eCRFs for a subject are associated with this de- identified ID.

16.2. Data Storage

The clinical database management system (CDMS) is the electronic data capture (EDC) system Medrio. The Medrio EDC system is developed and hosted by Medrio, Inc. The Medrio EDC system meets CFR 21 Part 11 compliance. Study data will be sent to and securely stored in a central location of Medrio's servers for analysis in the United States (Dallas Texas, Seattle, Washington, and Washington D.C.).

16.3. Confidentiality

Patient confidentiality is strictly held in trust by the participating investigators, their staff, and the sponsor, and their agents. This confidentiality is extended to cover testing of biological samples in addition to the clinical information relating to study subjects. Therefore, the study protocol, documentation, data, and all other information generated will be held in strict confidence. No information concerning the study or the data will be released to any unauthorized third party without prior written approval of the sponsor.

The study monitor, other authorized representatives of the sponsor supplying the study device, representatives of the ethics committee may inspect all documents and records required to be maintained by the investigator, including but not limited to, medical records (office, clinic, or hospital) and pharmacy records for the subjects in this study. The clinical study site will permit access to such records.

The study subject's contact information will be securely stored at each clinical site for internal use during the study. At the end of the study, all records will continue to be kept in a secure location for as long a period as dictated by IRB and institutional regulations.

Study subject research data, which is for purposes of statistical analysis and scientific reporting, will not include the Patient's contact or identifying information. Rather, individual patients and their research data will be identified by a unique study identification number.

CT images, KUB X-Ray and ultrasound images will be obtained for study evaluation. If published, study subject-identifying information will be removed.

CONFIDENTIAL Page 46 of 53

16.4. Study Record Retention

All study records and reports will remain on file at the sites for a minimum of 2 years after completion of the Study and will further be retained in accordance with local guidelines as identified in the clinical study agreement. Study records are to be discarded only upon notification by the study sponsor. The Investigator must contact the study sponsor before the destruction of any records and reports pertaining to the study to ensure they no longer need to be retained. In addition, the sponsor should be contacted if the Investigator plans to leave the investigational site. All required data for this study will be collected on standardized CRFs or an electronic data capture system.

All information and data sent to the Sponsor or Contract Research Organizations (CROs) concerning subjects or their participation in this study will be considered confidential. All data used in the analysis and reporting of this evaluation will be used in a manner without identifiable reference to the subject. The Principal Investigator consents to visits by the staff of the Sponsor and its authorized representatives and the U.S. Food and Drug Administration or any other local governmental body to review the study subjects' medical records including any test or laboratory data that might have been recorded on diagnostic tests media (e.g., CT scans, X-rays, etc.).

17. USE OF DATA, PUBLICATIONS POLICY, REGISTRATION

To safeguard the integrity of the study, reports (summary or interim) will not be submitted for publication without prior agreement from Applaud Medical, Inc.

Anonymized subject data may be used for publication and presentation purposes. Photos and audio/visual recording of the procedure may be performed at the investigator's discretion. It may be used for professional publication or presentation purposes if the information is anonymized and it is covered by the subject's informed consent.

The study will be registered on https://clinicaltrials.gov in compliance with 42 CFR Part 11. Results of the study, including an unanticipated early termination of the trial, will be posted to the Clinicaltrials.gov database at the conclusion of the study.

CONFIDENTIAL Page 47 of 53

В	DCO-243	15 APR 2021	 Section 5.8 and protocol synopsis section: An exclusion criterion of "Patients who have had prior URS-LL within 3 months on the side to be treated at the time of consent" is added to minimize/prevent confounding clinical outcomes in the analysis of data. Section 5.8 and protocol synopsis section: Exclusion criterion "If female, last menstrual cycle(s) is >30 days on the study procedure unless patient has a documented history of menstrual cycle(s) that are absent or are >30days if not pregnant" is removed since all females will be required to take a pregnancy test on the day of the procedure. Protocol Synopsis section: Added Abond CRO, Inc. information. Abond CRO will be responsible for managing the AEROLITH study's data and conducting statistical analysis. Section 5.5: added the words "and randomized" and "subjects" for clarity. This language, added for clarity, is consistent with the language in the original IDE protocol. Section 6.3.2: Reworded section to "Re-interventional procedure(s) on stone(s) that were treated as part of the AEROLITH study" for clarity. Section 6.4.2 "Subjects will be blinded of their treatment allocation through index procedure" was added as a measure to minimize bias. Section 7.3: Changed the timing of randomization from after subject receives general anesthesia to randomizing a subject the day of the procedure. The rationale for this change is to minimize logistical challenges of unnecessarily transporting temperature sensitive investigational devices to the Operating Room (OR) if it's not needed. Further, this minimizes or prevents an incident of not being able to secure a randomization number from the EDC if the OR does not have a computer or Wifi connectivity. To maintain the scientific soundness of the study, subjects will still be blinded of their treatment allocation through index procedure. Section 7.5: added subject identification coding system. Sections 8.5. A

CIP-0001(E) Acoustic Enhancer Research on Laser Lithotripsy (AEROLITH) Clinical Study DCO-326 EFFECTIVE DATE: 19 JAN 2022

> **CONFIDENTIAL** Page 50 of 53

·  	-	Acoustic Enhancer Research on Laser Lithotripsy (AEROLITH) Clinical Study				
			 Table 2: Updated table to be consistent with the protocol required tests and clarified language. Section 10.3: Added the word "randomized" for clarity. This is consistent with the language in the IDE clinical protocol approved by FDA. Section 10.8: Clarified language by adding words "subsequent" and "in the AEROLITH study" 			
c	DCO-288	22 AUG 2021	 Protocol Synopsis_Inclusion Criteria 6 – modified requirement of Urine culture. Principal Contacts Updated Study Statistician and Data Management from Abond to ARA Added [name] as Medical Monitor Sections 5.7.6 - modified requirement of Urinalysis with Urine culture. Section 8.1 modified requirement of Urinalysis with Urine culture. Section 8.2 - modified requirement of Urinalysis with Urine culture. Section 8.4, 8.5, and 8.6 - modified requirement of Urinalysis with Urine culture. Rationale for modifying requirement of Urine culture – Per AUA Guidelines, Urine culture is conducted only if patient presents with positive urinalysis and/or clinical signs of an infection. 			
D	DCO-306	12 NOV 2021	 Section 5.1.1 was updated to reflect the recent approval for full enrollment to a total of 196 subjects per G200183/S007. Protocol synopsis and Section 5.5, added "each site may enroll no more than 20% of the total sample size of 196 subjects." to address FDA's study consideration detailed in G200183/A001. Protocol synopsis, Section 5.7.3.2 and 5.8.1, added a note that punctate stones measuring ≤2mm do not count in the 3 stone limit or in the cumulative diameter limit of 20mm for clarity to align with the language in CLIN-0003: Radiographic Evaluation Protocol for the AEROLITH Study, previously approved by FDA (G200183/A001). In Section 4.1.1 of CLIN-0003, it states "Any renal calculi less ≤ 2 mm in diameter (largest diameter in any plane), and/or maximum CT intensity < 100 HU will not be counted as stones." Protocol synopsis and Sections 5.8.2, deleted "Patients with >3 stones with a cumulative diameter of > 20mm on the side to be treated". Redundant, noted in 5.8.1 Protocol synopsis and Sections 5.8.7 and 8.1, added an exception to the rule where if recently tested (within 30 days of consent) urine pH is <5.5 but patient has his/her largest stone measuring a mean stone intensity of ≥500HU and has a historical pH value of ≥ 5.5, patient may qualify for the study. AEROLITH study investigators have advised Applaud that urine pH isn't always predictive of a calcium-based stone (which is the intended stone for treatment by the Acoustic Enhancer) since urine pH can be influenced by diet, diseases, medications and timing of urine pH testing. AEROLITH investigators and Applaud's Advisors are proposing that the largest stone intensity is factored into the determination of calcium-based Stones for those patients who fail to meet the pH threshold during the screening process. Applaud's Advisors and AEROLITH investigators propose that these patients may be considered if his/her largest stone intensity ≥ 5.5. Protocol synopsis section and Section 6.1, defined the pr			

CIP-0001(E) Acoustic Enhancer Research on Laser Lithotripsy (AEROLITH) Clinical Study DCO-326 EFFECTIVE DATE: 19 JAN 2022

> **CONFIDENTIAL** Page 51 of 53

	1		Research on Laser Lithotripsy (AEROLITH) Clinical Study
			 seriousness, and relatedness to align with the requirement in Section 6.4.3 Defined and added Study Success in the protocol synopsis and Section 6.6 to address FDA's study consideration detailed in G200183/A001. Section 6.2, added "the primary efficacy endpoint will demonstrate that the investigational arm is superior in the fragmentation of stones versus the control arm." to align with Applaud's proposal of a superiority statistical design for primary efficacy endpoint. Section 6.3, added "the secondary efficacy endpoint will demonstrate non-inferiority of the mean TRE used between the investigational and control arm to align with Applaud's proposal of a non-inferiority statistical design for the secondary endpoint. It is worthy of note that statistical significance with this secondary efficacy endpoint along with any other effectiveness endpoints are not needed for study success. Section 6.4.2 changed the language from "re-interventional" to "additional interventional stone procedure" for clarity.
			• Sections 10.5 and 10.7, modified the secondary hypotheses 1 and 2 to align with
Ε	DCO-326	19 JAN 2022	 the secondary endpoint statistical design. Inclusion criterion no. 3 of the protocol synopsis and section 5.7.3 are modified to allow patients having multiple stones (>3 stones). The stone cumulative diameter limit does not change and remains 20mm as recommended for URS-LL by the Surgical Management of Stones: AUA/Endourology Society Guideline (2016) as follows: "21. In symptomatic patients with a total non-lower pole renal stone burden of ≤ 20mm, clinicians may offer SWL or URS. (Index Patient 7) Strong Recommendation; Evidence Level Grade B." This is being modified to reflect typical kidney stone population that would be eligible for URS-LL. Inclusion criterion no. 3 of the protocol synopsis and section 5.7.3, added "Note 2: Some corroborating imaging may be required to exclude a patient if the investigator suspects that the stone has moved to middle/distal ureter (e.g. change in symptoms, an increase in serum creatinine)" This ensures that those patients whose stones are suspected to have moved (after being found eligible for the study) to middle/distal ureter and may require other form of treatment/management are excluded from the study. This aligns with the Surgical Management of Stones: AUA/Endourology Society Guideline (2016) as follows: "8. Clinicians should offer reimaging to patients prior to surgery if passage of stones is suspected or if stone movement will change management. Reimaging should focus on the region of interest and limit radiation exposure to uninvolved regions. Clinical Principle" Inclusion criterion no. 4 of the protocol synopsis and section 5.7.4 are modified to extend the baseline CT image cut off from 30 to 60 days. In Rev. D of the protocol, a patient is required to have a repeat CT scan if their CT image is >30days old. The purpose of this change is to reduce the radiation exposure of patients with >30days CT scan having to undergo a repeat CT image. Exclusion criterion no. 1 of the protocol synopsis and

CIP-0001(E) Acoustic Enhancer Research on Laser Lithotripsy (AEROLITH) Clinical Study DCO-326 EFFECTIVE DATE: 19 JAN 2022

> **CONFIDENTIAL** Page 52 of 53

	exceed 20mm.	
	• Exclusion criterion no. 7 of the protocol synopsis and section 5.8.7, added the	
	words "the patient" for clarity.	
	• Exclusion criterion no. 11 of the protocol synopsis, section 5.8.11, section 8.2	
	and Table 2, added serum testing as an alternative pregnancy test method.	
	• Section 8.2, added "and prior to randomization" for clarity.	
	• Section 8.2, updated section for clarity and to ensure alignment with the	
	Acoustic Enhancer IFU (LBL-014, Rev. F.), which was approved by FDA under	
	G200183/S005.	
	• Section 10.2, expanded the definition of ITT for clarity and to ensure that in the	
	event a subject develops UTI or has his/her stone moved to the middle/distal	
	ureter or who no longer meet any of the other inclusion/exclusion criteria	
	between the time the subject was initially found eligible and the time they were	
	randomized, are not treated under the protocol and are excluded from the	
	study.	
	• Protocol Synopsis and Section 5.0: Update number of investigational sites to 18	
	per G200183/S011	

CONFIDENTIAL Page 53 of 53

1 INTRODUCTION

This statistical analysis plan (SAP) describes the planned analysis and reporting for Applaud Medical's protocol number CIP-0001: Evaluation of Applaud Medical's Acoustic Enhancer with Laser Lithotripsy in the Treatment of Urinary Stones, revision E, dated 19Jan2022. This SAP will be signed off, at a minimum, before the final database lock and contains detailed information to aid in the performance of the statistical analysis and reporting of the study data for use in the final clinical study report (CSR). This SAP is being written with due consideration of the recommendations outlined in the most recent International Conference on Harmonization (ICH) E9 Guideline entitled Guidance for Industry: Statistical Principles for Clinical Trials and the most recent ICH E3 Guideline and the Guidance for Industry: Structure and Content of Clinical Study.

This SAP describes the data that will be analyzed and the subject characteristics, safety, and efficacy assessments that will be evaluated. This SAP provides details of the specific statistical methods that will be used. If additional analyses are performed after database lock and unblinding to supplement the planned analyses described in this SAP, they will be clearly identified as post-hoc in the CSR.

In addition to the study protocol, the case report forms (CRFs) were reviewed in preparation of this SAP.

The reader of this SAP is encouraged to also read the clinical protocol for details on the planned conduct of this study. Operational aspects related to collection and timing of planned clinical assessments are not repeated in this SAP unless relevant to the planned analysis.

1.1 STUDY OBJECTIVES

The purpose of this pivotal study is to evaluate the safety and effectiveness of Applaud Acoustic Enhancer when used in conjunction with conventional ureteroscopic laser systems in the treatment of subjects with urinary stones.

2 STUDY DESIGN AND PROCEDURES

The clinical study is a prospective, multicenter, two-arm, randomized, double blinded study in male or female subjects 18 to 75 years of age with a diagnosis of urinary stone disease. For this study, double blinded means: 1) study subjects will not be informed of their treatment allocation through the index procedure, and 2) in assessing stone fragmentation using a CT image as defined in the primary endpoint, an independent radiologist will conduct the assessment and will be blinded to the treatment allocation of each subject's CT image.

The study visits consist of Screening, Treatment/Procedure [Day 1], Day 14 (+/- 4 days), Day 30 (+14 days), and Day 90 (+/- 21 days). Subjects who have unresolved hydronephrosis at Day 30 need to continue to Day 90. At 90-days post procedure, subjects who have on-going device and/or procedure-related serious adverse events (including device and/or procedure related hydronephrosis) and subjects with pre-existing (prior to treatment) hydronephrosis that have worsened or recurred will continue to be followed until the event has resolved or is deemed stable by the investigator prior to study exit. A total of 196 subjects will be enrolled in this study at up to 27 investigational sites located in the U.S., with each site enrolling no more than 20% of the total.

Following consent and if a subject meets the study's inclusion/exclusion criteria, the subject will be randomly assigned to the investigational arm (Acoustic Enhancer with URS-LL) or

control arm (URS-LL) on the day of the procedure. Random assignment will be conducted using an allocation ratio of 1:1 with one subject randomized to the investigational arm for each subject randomized to the control arm. A minimum of 176 evaluable subjects will be needed for analysis. After randomization and during procedure, eligibility criteria will be verified. If subjects are found to not meet eligibility criteria they will be considered screen failures and will not be considered randomized and treated for analysis purposes.

Random assignment will be conducted using a stratified permuted block design generated separately for each clinical site.

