7.3. Randomization Assignment: Acoustic Enhancer with Ureteroscopic Laser Lithotripsy (Investigational Arm) vs. Standard Ureteroscopic Laser Lithotripsy (Control Arm)

Following consent and if a subject meets the study's inclusion/exclusion criteria, the subject will be randomly assigned to the investigational or control arm on the day of the procedure. If the potential subject does not meet the study procedure eligibility criteria, he/she will NOT be randomly assigned to treatment or the control arm. Random assignment will be conducted using an allocation ratio of 1:1 with one subject randomized to the Investigational Arm for each subject randomized to the Control Arm. Random assignment will be conducted block design generated separately for each clinical site. Subjects will be blinded to treatment allocation through index procedure.

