10.2. Analysis Population

The study results will be summarized based on three populations:

Intent-to-Treat (ITT): The ITT population consists of all randomized subjects who meet the study inclusion/exclusion criteria. Subjects who develop UTI or having their stone move to the middle/distal ureter between the time they were screened and were found to be eligible at the time they were randomized, or who no longer meet any of the other inclusion/exclusion criteria at the time of the procedure, will not be treated under the protocol. These subjects will not be included in the ITT analysis. The ITT population will be used for all effectiveness analyses with groups based on the randomized treatment.

Safety Population: The Safety population consists of all subjects who had a procedure performed. The Safety population will be used for the safety summaries (adverse events or strictures) with groups based on the actual treatment received.

CONFIDENTIAL Page 32 of 53

Acoustic Enhancer Research on Laser Lithotripsy (AEROLITH) Clinical Study

Per-Protocol Population (PP): The Per-Protocol population will consist of all subjects who complete the primary endpoint information without a major protocol deviation; PP will include subjects who have evaluable CTs both at baseline and at 30-day follow-up. The PP population analyses will be completed based on the randomized treatment arm.

The definition of major protocol deviations will be defined prior to any final analysis. Subjects who are screened but not randomized will not be included in analysis. Any information on these subjects will be made available in a listing if requested by the IRB or FDA.

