6 SUBJECT SUMMARIES

6.1 ANALYSIS POPULATIONS

6.1.1 Intent-to-Treat (ITT) Population

The ITT population consists of all randomized subjects who meet the study inclusion/exclusion criteria. Subjects who develop UTI or having their stone move to the middle/distal ureter between the time they were screened and were found to be eligible at the time they were randomized, or who no longer meet any of the other inclusion/exclusion criteria at the time of the procedure, will not be treated under the protocol. These subjects will not be included in the ITT analysis. The ITT population will be used for all effectiveness analyses with groups based on the randomized treatment.

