6.1.2 Per-Protocol (PP) Population

The Per-Protocol population will consist of all subjects who complete the primary endpoint information without a major protocol deviation; determination of protocol deviation severity will follow Sponsor procedure, CAP-0017. PP will include subjects who have evaluable CTs both at baseline and at 30-day follow-up. The PP population analyses will be completed based on the randomized treatment arm. The PP population may be used for all effectiveness analyses as sensitivity analyses with groups based on the randomized treatment.

The definition of major protocol deviations is defined in CAP-0017. The list of deviations will be reviewed, and deviations that will exclude subjects from the PP population will be identified and documented in an Excel file that will be approved by the Sponsor. The approved Excel file will be incorporated into analysis programming and used to exclude subjects from the PP population. Subjects who are screened but not randomized will not be included in analysis. Subjects who were randomized but failed screening intraoperatively will not be included in the analysis. Any information on these subjects will be made available in a listing if requested by the IRB or FDA.

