6.1.3 Safety Population

The Safety population consists of all subjects who had a procedure performed. The Safety population will be used for the safety summaries (AEs) with groups based on the actual treatment received.

6.2 **PATIENT DISPOSITION**

The number of subjects included in each analysis population (ITT, Safety, and PP) will be summarized by treatment group and overall for all randomized subjects. The number of subjects screened, enrolled, randomized, randomized and not treated, completed the study, and discontinued the study early (including the reasons for discontinuation such as randomized and not treated due to a screen failure) will be summarized for each treatment group and overall.

Subjects who are excluded from an analysis population will be summarized by the reasons for exclusion by treatment group and overall.

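### The set called ITT drops randomized subjects found ineligible at or during the procedure, with no limit to pre-randomization facts and no requirement to judge them blind to arm

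*SAP*

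**What the plan says.** **Analysis set.** Protocol 10.2 and SAP 6.1.1 give the same definition: ITT is the randomized subjects who satisfy the inclusion and exclusion criteria. Of this set the protocol says "The ITT population will be used for all effectiveness analyses with groups based on the randomized treatment". Two named reasons for removal, UTI and stone movement to the middle or distal ureter, are placed between screening and randomization, although the sentence is awkward. A catch-all follows for subjects "who no longer meet any of the other inclusion/exclusion criteria at the time of the procedure, will not be treated under the protocol"; they are left out of ITT.

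**Timing.** Under Protocol 7.3, "the subject will be randomly assigned to the investigational or control arm on the day of the procedure". SAP 2 then says "After randomization and during procedure, eligibility criteria will be verified", and of those who fail, "they will be considered screen failures and will not be considered randomized and treated for analysis purposes". SAP 6.1.2 adds: "Subjects who were randomized but failed screening intraoperatively will not be included in the analysis".

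**Stop before anesthesia.** Protocol 7.6 classes anyone discontinued before general anesthesia as a screen failure and leaves that person out of every endpoint analysis.

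**Blinding and oversight.** Protocol 7.4 and SAP 2 blind the subject (through the index procedure) and the CT reader. Protocol 12.1 requires decisions on excluding data to be made before database lock, with exclusions listed; it does not mention treatment arm. SAP 6.5 sets major deviations before unblinding, but for the per-protocol set.

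**Reporting.** SAP 6.2 tabulates, by arm, subjects "randomized and not treated due to a screen failure", and states: "Subjects who are excluded from an analysis population will be summarized by the reasons for exclusion by treatment group and overall".

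**The concern.** Randomization protects the comparison only while membership of the analysis set does not depend on what happens after allocation. Here a subject can be removed from the primary set after the arm is assigned, for any eligibility criterion, up to and including the procedure. Nothing says that the disqualifying fact must have existed before randomization, or that whoever decides must be unaware of the arm.

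That the operator knows the arm is an inference. Protocol 8.2 has the agent placed near the stone at intervals during lasering, and SAP 7 describes the procedure data as unblinded. No passage states it outright.

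If removals differ by arm and are related to outcome, the estimated difference in success is biased. Multiple imputation and the tipping-point analysis (Protocol 10.6) deal with missing responses inside the same reduced set, and the per-protocol set is narrower still. The exclusion tables would show unequal counts but not their effect on the result.

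**Working it through.** **1. The plan's own figure.** Inputs from Protocol 10.3 and SAP 3: control 55%, investigational 75%, one-sided 0.025, 88 evaluable per arm, 10% non-evaluable. With null-pooled variance (Farrington-Manning at zero margin):

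- SE under the null = √(2 × 0.65 × 0.35 / 88) = 0.0719
- SE under the alternative = √((0.75 × 0.25 + 0.55 × 0.45) / 88) = 0.0703
- Power = Φ((0.20 − 1.96 × 0.0719) / 0.0703) = 79.96%; exact enumeration gives 80.3%
- 176 / 0.9 = 195.6, rounded up to 196

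The sample size reproduces. The issue is the analysis set.

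**2. How wide is the exposed window?** Protocol 7.3 and 7.5 require the criteria to be verified before randomization. Protocol 8.2 and Table 2 put the pregnancy test, and any repeat urinalysis with the UTI symptom check, before randomization on the day. What remains is the catch-all at the time of the procedure, findings during the procedure, and stops between randomization and anesthesia.

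**3. Effect on type I error.** The documents give no removal counts or failure risks, so these are assumptions. Take 98 per arm, true success 55% in both, and remove k subjects with failure risk r = 0.70 from an arm:

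remaining rate = (98 × 0.55 − k(1 − r)) / (98 − k)

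For 5 vs 2 (investigational vs control): (53.9 − 1.5)/93 = 0.5634 and (53.9 − 0.6)/96 = 0.5552, a bias of +0.82 points. Exact binomial enumeration of the pooled z test at 1.96 gives:

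| Removed, investigational vs control | Bias (points) | One-sided type I error |
|---|---|---|
| 0 vs 0 | 0 | 2.62% |
| 3 vs 2 | +0.27 | 2.93% |
| 5 vs 3 | +0.55 | 2.90% |
| 5 vs 2 | +0.82 | 3.42% |
| 5 vs 0 | +1.34 | 3.96% |
| 2 vs 3 | −0.27 | 2.29% |

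Equal removal (3, 5 or 10 per arm, r from 0.45 to 1.0) gives 2.35–2.81%. This is a complete-case calculation; the planned primary analysis uses multiple imputation.

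**4. Sensitivity at the boundary.** Against control 48/88, the smallest significant investigational result is 61/88 (z = 2.02, p = 0.022). Restoring one excluded investigational subject as a failure gives 61/89: z = 1.91, p = 0.028.

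**5. Subjects stopped before anesthesia.** Take a randomized subject who meets every criterion and withdraws before anesthesia. Under Protocol 10.2 and SAP 6.1.1 this subject is in ITT. Under Protocol 7.6 the same subject is in no endpoint analysis. Both cannot apply.

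**6. Power of an all-randomized analysis.** Assume 98 per arm, 10% of treated subjects without a CT, and untreated subjects counted as non-success. With none untreated there are 88 evaluable per arm and power is 80.3%. With one untreated there are 87 evaluable plus one failure: rates 0.75 × 87/88 and 0.55 × 87/88 with 88 per arm, power 79.1%. With two it is 77.8%.

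**The case against.** The strongest reply is that this is a deliberate, prespecified definition, explained in the Rev E history and identical in both documents; that the main checks precede allocation; that most criteria are baseline facts with no evident link to arm; and that Protocol 12.1, the exclusion tables by arm and the SAP listings constrain and expose removals. All of that stands, and it keeps the likely effect small. It does not supply the missing time limit or any blinding to arm.

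The magnitude is also open to challenge. Small imbalances barely leave the range that discreteness alone produces: 5 vs 3 gives a slightly lower error than 3 vs 2 despite twice the bias, and at 60% failure risk 5 vs 3 gives 2.69%, inside the balanced-removal range. Only larger or one-sided removals move the error clearly, and no passage predicts those. This stands.

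A reader might infer more than the documents support:

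- **That SAP 2 contradicts SAP 6.2.** It does not. Not being considered randomized and treated is compatible with being tabulated as "randomized and not treated due to a screen failure"; one governs analysis sets, the other disposition.
- **That protocol and SAP define ITT differently.** They do not. The conflict is Protocol 7.6 against the shared definition.
- **That no exclusion is time-limited.** UTI and stone movement are tied to the period up to randomization.
- **That the trial has no all-randomized analysis.** SAP 4, 5 and 8 send the primary analysis and its sensitivity analyses to a separate plan. It was not available and may contain one.

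**Conclusion.** The point holds in limited form and should be fixed. As written, the catch-all in Protocol 10.2 and SAP 6.1.1 and the intraoperative rule in SAP 2 and 6.1.2 allow removal from the primary set after allocation, without restriction to earlier facts and without blinding to arm. The planned analyses in these two documents cannot show what such removals do to the result. Separately, Protocol 7.6 conflicts with the ITT definition for eligible subjects stopped before anesthesia.

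The size rests wholly on assumed counts and failure risks. Modest imbalance takes one-sided type I error from 2.6% to roughly 2.9–3.4%, and 4.0% needs five removals confined to the investigational arm. Balanced removal has no material effect, and an imbalance in the other direction lowers the error. The documents do not show that exclusions will depend on arm; they only fail to prevent it.

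**What to change.** 1. In Protocol 10.2 and SAP 2, 6.1.1 and 6.1.2, limit exclusions after randomization to eligibility facts that existed before randomization, even if found later. Have them adjudicated blind to arm and outcome before database lock.
2. Unless the separate primary plan already has it, add one prespecified all-randomized sensitivity analysis of the primary endpoint, analysed as randomized. State the outcome rule for untreated subjects, because success is defined after an index procedure that they did not have; for example, multiple imputation and, separately, non-success. Keep the current set as primary.
3. Reconcile Protocol 7.6 with Protocol 10.2 and SAP 6.1.1 for eligible subjects stopped between randomization and anesthesia.

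Optional: call the current set modified ITT, and state how a subject who is anesthetised but later labelled a screen failure is handled in the Safety population.

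The cost is wording, a blinded review of exclusions by existing staff, and one extra analysis. With non-success imputed, that analysis has slightly less power than the primary: about 79% against 80% with one untreated subject per arm and 10% missing CT. That is why it is proposed as a sensitivity analysis only.
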